2.1.3 Recruitment Strategies

This protocol may be abstracted into a plain language announcement posted on NIH websites and on NIH social media platforms. Participants may also be recruited through self-referrals, physician referrals, and referrals from the NIH Clinical Center (CC) Office of Patient Recruitment.

2.2 RESEARCH ELIGIBILITY EVALUATION

Note: Screening evaluation testing/procedures are conducted under the separate screening protocol 06C0014 (Prospective Evaluation of Genetic and Epigenetic Alterations in Patients with Thoracic Malignancies).

Pre-treatment blood tests should be performed within one week and imaging studies **within 4 weeks prior to enrollment** on the trial unless otherwise stated. The evaluations required prior to starting treatment are listed in table form in [Appendix 2: Study Calendar](#).

- Complete history and physical examination including assessment of vital signs and ECOG status
- Laboratory
 - ROUTINE LABS:
 - Complete blood count, differential
 - Chemistries: LDH, SGPT (ALT), SGOT (AST), alkaline phosphatase, bilirubin (total and direct), BUN, creatinine, amylase, lipase, electrolytes, ionized calcium, magnesium, phosphorus, uric acid, albumin
 - Total and fractionated serum bile acids
 - Thyroid panel
 - HIV, HBV and HCV serologies
 - Affymetrix Drug Metabolizing Enzymes and Transporters (DMET) microarray genotyping of PBMC (to be performed in [name] lab under protocol 06C0014). (**May be performed at any time prior to enrollment.**)
 - Urinalysis
 - Women of child-bearing potential will have a urine or serum β -hCG pregnancy test.
 - Note: This test is to be done within 48 hours prior to start of treatment.
 - Coagulation Studies: PT/PTT/Thrombin Time/Fibrinogen, PFA-100, VWF antigen, VWF activity, Factor VIII activity, D-dimer, Fibrin degradation products and FXIII activity.
- Radiographic Evaluation

Assessment of disease sites by appropriate radiological evaluation. This should include a CT scan of chest, abdomen and pelvis, brain MR and PET-CT. Ultrasonographic elastography of liver (all patients).
- Arterial blood gas (ABG) if clinically indicated
- Pulmonary function tests (PFTs)

- Cardiac Function Studies
 - Assessment of cardiac function (ejection fraction/shortening fraction) must be performed within 4 weeks of enrollment by MUGA, Echocardiogram, or cardiac MR to rule out cardiomyopathy.
 - A 12-Lead electrocardiogram (EKG) will also be performed.
- Pathologic/Tissue Evaluation

Histologic confirmation of tumor by the NCI Laboratory of Clinical Pathology, NIH (may be performed at any time prior to registration).

2.3 PARTICIPANT REGISTRATION AND STATUS UPDATE PROCEDURES

Registration and status updates (e.g. when a participant is taken off protocol therapy and when a participant is taken off-study) will take place per CCR SOP ADCR-2: CCR Participant Registration & Status Updates found [here](#).

2.4 TREATMENT ASSIGNMENT PROCEDURES

Cohorts

Number	Name	Description
1	Phase I	Patients with primary malignancies involving lungs, esophagus, thymus, pleura, chest wall or mediastinum, or extra-thoracic malignancies metastatic to the chest
2	Phase II (Thoracic Malignancies)	Patients with primary thoracic malignancies
3	Phase II (Non-Thoracic Malignancies)	Patients with neoplasms of non-thoracic origin metastatic to the chest

Arms

Number	Name	Description
1	Phase I	Escalating doses of Mithramycin
2	Phase II	Mithramycin administered at MTD

Arm Assignment

- Up to 54 patients in Cohort 1 may be initially assigned to Arm 1 until MTD is determined.
- After MTD is determined:
 - Up to 7 evaluable patients in Cohort 2 will be directly assigned to Arm 2. An additional 14 may be directly assigned if interim efficacy analysis is positive.
 - Up to 7 evaluable patients in Cohort 3 will be directly assigned to Arm 2. An additional 14 may be directly assigned if interim efficacy analysis is positive.

3 STUDY IMPLEMENTATION

3.1 STUDY DESIGN

This Phase I/II study is designed primarily to evaluate the toxicities, pharmacokinetics and clinical efficacy of mithramycin administered as a continuous 24-hour infusion in patients with thoracic malignancies. All patients will be evaluated initially in the Thoracic Surgery Clinic, Clinical Center, NIH. Once appropriate consents have been signed, patients will undergo biopsy of their tumors for analysis of pharmacodynamics endpoints via endoscopic procedures performed in the operating room by the Thoracic Surgery attending physicians or by percutaneous FNA methods performed by interventional radiology staff at the Clinical Center, NIH. Specimens will be processed for DNA/RNA isolation, and immunohistochemistry studies. If sufficient materials are available from a previous biopsy either at the NIH or elsewhere, this baseline biopsy may be omitted as outlined in [Appendix 2](#). Patients will be hospitalized on 3NW, NIH Clinical Center, and receive 24h infusions of mithramycin as outlined below using a conventional Phase I study design, with no intra-patient dose escalation, and no routine cytokine support. Treatment cycles will be separated by 2 weeks to allow recovery from systemic toxicities. Due to potential cardiac toxicity related to mithramycin, all patients will have EKGs (12 lead) prior to, and daily EKGs for 4 days following mithramycin infusions (first cycle only unless otherwise clinically indicated), and will be on telemetry during the Cycle 1 infusion (and subsequent cycles if clinically indicated per Cardiology recommendations). Patients will also have routine bloodwork as outlined in [Section 3.5](#). Blood will be obtained at designated time points to assess mithramycin levels are outlined in [Section 5.1](#). Unless medical difficulties arose during the collection of the first biopsy, a post-treatment tumor biopsy will be obtained on Cycle 1 Day 4 (+/- 3 days) to assess molecular endpoints. At the time of each biopsy session, representative samples will be evaluated by frozen section techniques to verify the histology and quality of the tumor tissue for subsequent analysis. An attempt will be made to biopsy the same tumor site for consistency of sampling during the treatment cycles. Approximately 14 days following initiation of the first treatment cycle, a second treatment cycle will commence. If possible, an optional tumor biopsy may be taken at treatment evaluation following the end of Course 1, and additional optional tumor biopsies requested if a patient experiences a dramatic clinical response to treatment, provided that the biopsies are easy to obtain and pose little risk to the patients (refer to [Section 5.2](#) and [Appendix 2](#)). CT guided research biopsies will not exceed 5 per year on this study. At the end of the fourth cycle (approximately 56-60 days following the initiation of the first treatment cycle), patients will return to the Thoracic Surgery Clinic for repeat staging studies and blood work to analyze treatment response using criteria outlined in [Section 6.3.3](#). In patients who exhibit response to therapy and commence a second course of mithramycin treatment an additional tissue biopsy may be requested during this course of therapy for confirmatory analysis of pharmacodynamics endpoints identified in preclinical experiments to be associated with regressions of human cancer xenografts in mice.

Summary of Mithramycin Treatment Cycle 1

	Day 1	Day 2	Day 4	Day 15
Initial Evaluation including imaging, blood work and biopsy of tumor tissue for molecular analysis*	Commence Mithramycin Infusion	Complete Mithramycin Infusion	Tumor Biopsy in OR or Interventional Radiology Suite	Commence Second Cycle.

Obtain blood for Pharmacokinetic Studies

→
and Toxicity Analysis as outlined in Sections 3.5 and 5.1

*May be obtained at any point prior to treatment either on this protocol or from clinically indicated procedures (surgeries and/or biopsies) obtained on 06C0014. If sufficient tissue is available from a biopsy performed at a previous time at NIH or elsewhere, this baseline biopsy may be omitted.

Note: Blood work will be collected as described in Section 3.5.

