3.2 DRUG ADMINISTRATION

Given our recent findings within our recent Phase II mithramycin trial (12C0151) pertaining to ABCB4, ABCB11, RALBP and CYP8B1 SNPs that distinguish patients who did and did not experience mithramycin-mediated hepatotoxicity, this protocol will accrue only those patients with favorable ABCB4/ABCB11/RALBP/CYP8B1 genotypes.

Mithramycin will be administered intravenously via central line over 24 hours once every 14 days (+7 days/-3 days). 12 mg IV of dexamethasone will be administered one hour prior to each infusion. Four cycles will constitute one course. Intravenous hydration will be provided as clinically indicated.

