5.2 STUDIES ON TUMOR TISSUE

Tissue biopsies will be obtained by minimally invasive methods such as CT guided percutaneous, endoscopic, laparoscopic or video-assisted thoracoscopic techniques at baseline* if sufficient tissue is not available from a previous biopsy (all efforts will be made to avoid repeat biopsy) and on Cycle 1 Day 4 (\pm 3 days). If possible, an optional biopsy may be taken at treatment evaluation

following Course 1. If insufficient tissue was obtained or if there was harm associated with the first biopsy, a second biopsy will not be obtained. Should a patient experience a dramatic clinical response to treatment, additional tumor tissue biopsies may be requested, but are not required (refer to [Appendix 2](#)). At the time of tissue acquisition, immediate on-site cytopathologic analysis will be performed to confirm that malignant cells are present in the biopsies, to enhance potential yield and improve subsequent evaluation of molecular endpoints. Samples will be placed in saline in an orange top tube on wet ice and transported to the Thoracic Epigenetics Lab for further processing.

In the Thoracic Epigenetics Lab, a portion will be separated and frozen on dry ice for RNA collection for focused microarray and/or qRT-PCR analysis of ~50 genes modulated by mithramycin in murine xenograft experiments. If sufficient tissue is available, another portion will be imbedded in paraffin for subsequent immunostaining experiments, focusing on expression of genes correlating with treatment response in our preclinical experiments. Additional tissue will be used to establish cell lines to examine effects of mithramycin on the epigenome and stem cell signaling *in vitro*, in an attempt to correlate these findings with results obtained from analysis of tumor biopsies, or to examine SP. All of the analyses, which are predicated on acquisition of sufficient biopsy materials, will be performed in the Thoracic Epigenetics Lab under direction of the PI.

Note: If there is an optional biopsy for research in the protocol, then the patient will consent at the time of the procedure. If the patient refuses the optional biopsy at that time, the refusal will be documented in the medical record and in the research record.

* May be omitted as outlined in [Appendix 2: Study Calendar](#).

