10.3 SECONDARY ENDPOINTS

Pharmacokinetic analysis will be conducted using non-compartmental methods. For pharmacodynamic endpoints, descriptive statistics will be used for each endpoint. Briefly, pharmacokinetics and molecular endpoints in target tissues will be assessed before and after mithramycin treatment, with the primary focus being comparison of microarray, qRT-PCR and IHC results relative to profiles identified in our preclinical studies. It is anticipated that non-parametric statistical methods will be used to compare paired results before and after treatment (but not between groups), as well as to perform comparisons or correlations among parameters. As the exact set of comparisons and analyses to be performed will be determined following

completion of the trials, and will be based on limited numbers of patients, the analyses will be considered exploratory and hypothesis generating rather than definitive. The results of these descriptive analyses will be used to design further studies.

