A. Propidium iodide staining demonstrating that 24 hour MM treatment induces dose dependent G0/G1 arrest in MPM cells.

B. β -galactosidase staining assays demonstrating that 24 hour MM treatment induces dose dependent senescence in MES1 and MES7 cells.

C. and D. Apo-BrdU analysis demonstrating minimal apoptosis in MPM cells immediately following 24 hour MM exposure (C), but significant dose-dependent apoptosis 48 hours following drug treatment (D).

[figure not shown]
7A

Mithramycin Induces Hepatotoxicity in Some Cancer Patients

7B

Mithramycin Plasma Concentration vs Time (20 cycles, 12 pts)

[figure not shown]
- Peak and steady state concentrations were lower than predicted
- No significant differences in PK were apparent in patients with or without hepatotoxicity

Abbreviated Title: 24 h Mithramycin Infusion
Version Date: 12/22/2020

14.2.7 Figure 7: AST and ALT Levels and Representative Liver Biopsy from Patients with Mithramycin Mediated Hepatotoxicity. Transaminitis was Associated with Apoptotic Hepatocyte Death.

[figure not shown]
8A

Mithramycin-Induced Hepatotoxicity Correlates with ABCB4 SNP

[figure not shown]
[figure not shown]
[figure not shown]
[figure not shown]
[figure not shown]
[figure not shown]
8B

[figure not shown]
ABCB4 and ABCB11 Regulate Bile Acid Flow

Abbreviated Title: 24 h Mithramycin Infusion
Version Date: 12/22/2020

[figure not shown]
14.2.8 Figure 8: Results of DMET Analysis Demonstrating that Mithramycin Mediated Transaminitis Correlates with SNPs in ABCB4 and ABCB11.

[figure not shown]

14.2.9 Figure 9: Results of DMET Analysis Depicting Associations Between AST and ALT Elevations with SNPs in ABCB4, ABCB11, PEPT2, and RALB from Patients Receiving Mithramycin.

Estimated Mithramycin Plasma Concentrations during and after 24h Infusion

14.2.10 Figure 10: Simulated Mithramycin Plasma Levels During and After 24 Hour Infusion Based on Direct Quantitation of Mithramycin Plasma Levels from the Recent Phase II Mithramycin Trial (Grey Dots).

14.2.11 Figure 11: Observed and Predicted Mithramycin Plasma Levels Following 24 Hour Mithramycin Infusions.

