Note: Day 1 labs can be drawn on the day prior to treatment infusion. In between treatments, monitoring lab evaluations may be drawn twice weekly (+48 hours between labs). For patients not experiencing Grade 3 or 4 toxicities these labs may be drawn once weekly in between treatments per PI discretion instead. (See Section 3.5.2)

^c Cycle 1 only (+/- 3 days).

Cycle 2 and beyond*								Follow-up Evaluations ^h	
Week 1							Week 2		
Day 1	Day 2	Day 3	Day 4	Day 5	Day 6	Day 7	Day 8	Day 11	Day 14
^d Cycle 2 and beyond, on Day 1 +/- 3 days.									
^e Baseline biopsies may be obtained at any point prior to treatment (pre-infusion) either on this protocol or from clinically indicated procedures (surgeries and/or biopsies) obtained on 06C0014. If sufficient tissue is available from a biopsy performed at a previous time at NIH or elsewhere, the baseline biopsy may be omitted.									
The Cycle 1 Day 4 (+/- 3 days) biopsy is required.									
If possible, an optional biopsy may be taken at treatment evaluation following Course 1. Should a patient experience a dramatic clinical response to treatment, additional optional tumor tissue biopsies may also be requested but are not required (refer to 5.2). These biopsies will only be performed if they are easy to obtain and pose little risk to the patient.									
Note: CT-guided research biopsies are not to total more than 5 in one year on this study.									
^f See Appendix 3 for PK timepoints.									
^g Done within 2 hours pre-infusion.									
^h After completion of last treatment cycle, CBC chemistries and coagulation studies are monitored weekly until resolution of toxicities; Patients with stable disease or responding to therapy will undergo CBC, chemistries, coagulation studies, history, physical exam and tumor measurements (CT scan of the chest, abdomen and pelvis, PET/CT and brain MR without gadolinium contrast) every 2 months until off study criteria are met.									
ⁱ End of course. 1 course = 4 cycles. Evaluation performed within +/- 2 weeks of end of course. At the end of course radiographic evaluation: CT scan (C/A/P) (with standard oral/IV contrast), PET/CT scan, and brain MR without gadolinium contrast; tumor measurements will be performed after every course of therapy (four cycles, 8 weeks +/- 2 weeks).									

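### Tumour-tissue pairs may use baseline tissue older than other anticancer therapy, or a follow-up biopsy taken before the infusion ends, and Section 10.3 has no rule for either

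*Combined protocol and SAP*

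**What the plan says.** **Baseline tissue.** The footnote to the Cycle 1 summary in Section 3.1 says of baseline tissue: "May be obtained at any point prior to treatment either on this protocol or from clinically indicated procedures (surgeries and/or biopsies) obtained on 06C0014". It continues: "If sufficient tissue is available from a biopsy performed at a previous time at NIH or elsewhere, this baseline biopsy may be omitted". Section 5.2 makes existing tissue the preferred source. A new baseline biopsy is taken "if sufficient tissue is not available from a previous biopsy (all efforts will be made to avoid repeat biopsy"). Appendix 2, footnote e, repeats the allowance. None of these places sets a maximum age or a condition on therapy given in between.

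**Follow-up tissue.** Section 3.1 states that "a post-treatment tumor biopsy will be obtained on Cycle 1 Day 4 (+/- 3 days) to assess molecular endpoints". Section 5.2 gives the same window, and Appendix 2 adds: "The Cycle 1 Day 4 (+/- 3 days) biopsy is required".

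**Infusion.** Section 3.2: "Mithramycin will be administered intravenously via central line over 24 hours once every 14 days (+7 days/-3 days"). The Cycle 1 summary starts the infusion on Day 1 and completes it on Day 2.

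**Analysis.** Section 10.3 anticipates that "non-parametric statistical methods will be used to compare paired results before and after treatment (but not between groups"). It leaves the exact comparisons until after the trial and calls them exploratory. It says nothing about tissue source, baseline age, intervening therapy or biopsy day.

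**The concern.** A paired before/after test reads the difference within a patient as the effect of what happened between the two samples. That reading is safe only if mithramycin is the main thing that happened, and if the second sample was taken after exposure.

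The first condition can fail. Criterion 2.1.1.6 requires first-line chemotherapy to have been received or refused, so many patients will have been treated between diagnosis and enrolment. The 30-day washout in 2.1.1.7 governs the start of dosing, not the date of the tissue. A diagnostic specimen from before chemotherapy can therefore be the baseline. Section 1.2 links ABCG2 expression to chemoresistance and a stem-like phenotype, so it is a reasonable inference, though not a documented fact, that intervening chemotherapy could move the genes being measured in either direction.

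The second condition can fail because the window opens with the infusion.

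The first two secondary objectives in 1.1.2 (inhibition of stem cell gene expression, and pre/post tumour profiles) rest on these pairs, and Section 10.3 says the results will be used to design further studies.

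**Working it through.** The plan states no sample size, alpha or power for the paired molecular comparison, so there is no figure of its own to reproduce.

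**Window.** 4 − 3 = Day 1 and 4 + 3 = Day 7. The infusion runs 24 h from Day 1 to Day 2. About the first 24 h of the permitted window therefore precedes the end of exposure. Tissue taken later on Day 2, after the infusion ends, is properly post-treatment.

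**Baseline interval.** The upper bound is the start of treatment; there is no lower bound.

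**What the test estimates.** Let δ be the true drug effect, f the share of pairs whose baseline predates an intervening therapy, Δ the shift that therapy caused, and g the share of follow-up biopsies taken before any effect is present. The expected mean paired difference is

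(1 − g)·δ + f·Δ.

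The second term is bias credited to the drug; the factor (1 − g) is dilution.

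**Illustration.** All of f, Δ, g, δ and the number of pairs are assumptions; the documents give none of them. The test is a two-sided 0.05 Wilcoxon signed-rank test on normal paired differences with SD 1, with 2,000 replicates. Fourteen pairs would be the first stage of both Phase II cohorts (2 × 7) and 42 their maximum (2 × 21), if every patient gave a usable pair; 20 lies between.

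- Intervening therapy, no drug effect (δ = 0, g = 0). With f = 0 the rejection rate is 0.04 to 0.06. With f = 0.5 it is:

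| Pairs | Δ = 0.25 SD | Δ = 0.5 SD | Δ = 1.0 SD |
|---|---|---|---|
| 14 | 0.08 | 0.12 | 0.29 |
| 20 | 0.07 | 0.17 | 0.45 |
| 42 | 0.11 | 0.33 | 0.82 |

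At f = 0.5 and Δ = 0.5 the apparent effect is 0.5 × 0.5 = 0.25 SD with an inert drug.

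- Early biopsies, true effect δ = 0.8 SD, f = 0, 20 pairs. Power is 0.92 at g = 0, 0.68 at g = 0.25 and 0.31 at g = 0.5. The mean shifts are 0.8, 0.6 and 0.4 SD. This counts an early biopsy as showing none of the effect, which is the worst case.

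The monotone pattern is the useful part; the individual values move with the assumptions.

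**The case against.** Much of the case on the other side stands.

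- **The plan limits its own claims.** The analyses are secondary, descriptive and declared hypothesis-generating. No decision rests on a p-value from them.
- **Using existing tissue spares patients a biopsy.** That is a stated choice and need not change.
- **A mid-infusion biopsy is probably not intended.** The nominal day is Day 4, the schema puts the biopsy after completion of the infusion, and the text calls it post-treatment. This is a drafting gap of about 24 h.
- **Blood-cell pairs are not affected by the baseline problem.** Section 3.5.1 and Appendix 3 tie research bloods to the weeks or hours before dosing.

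Three stronger readings are tempting and are not supported.

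- A reader might infer from Figure 6, which reports "minimal apoptosis in MPM cells immediately following 24 hour MM exposure (C), but significant dose-dependent apoptosis 48 hours following drug treatment (D"), that tissue taken soon after the infusion is uninformative. That figure concerns apoptosis in cultured mesothelioma cells. The planned endpoints are mainly expression, methylation and microRNA. For expression, Section 1.2 reports marked changes at the end of 24 h exposure and persistence for at least 16 h after drug removal. Section 1.3.1 describes reprogramming that lasts well beyond exposure.
- A reader might count Days 1 and 2 among the seven permitted days and treat the fraction as an expected error rate. It counts calendar days, not biopsies, and part of Day 2 is valid.
- A reader might say that biopsy day biases the comparison. Early sampling dilutes it; bias would need biopsy day to be related to patient or tumour features, and nothing in the documents suggests that.

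**Conclusion.** The point holds for tumour-tissue pairs only. As written, the plan accepts baseline tissue of any age, including tissue from before other anticancer therapy, and accepts a follow-up biopsy before exposure is complete. Section 10.3 would pool all such pairs. The result can misattribute the effect of intervening therapy to mithramycin and can understate a real effect.

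The size cannot be fixed from the documents. The share of pairs with pre-therapy baselines is not given; if it is zero, the first problem disappears, and patients with fresh baselines or no earlier therapy do not contribute to it. The number of biopsies during infusion may well be zero. The MTD and objective response results do not use these data. This is a worthwhile refinement of an exploratory analysis, not a threat to the trial. Parts of Sections 1.3.4 and 5.3.2 were not available to check.

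**What to change.** 1. **Section 10.3.** State, before any tumour molecular data are analysed, that the main paired tumour analysis uses pairs whose baseline tissue was taken after the last prior anticancer therapy, and that all pairs are reported as a sensitivity analysis. A patient with no prior therapy qualifies with any pre-treatment tissue.
2. **Data collection.** Record baseline biopsy date and site, anticancer therapy between baseline tissue and Day 1, and hours from the end of the Cycle 1 infusion to the follow-up biopsy.
3. **Sections 3.1 and 5.2 and Appendix 2.** State that the follow-up window opens once the Cycle 1 infusion is complete and runs through Day 7, so that Day 2 tissue taken after the infusion is kept.

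The cost is a few sentences, three or four data fields, fewer pairs in the main exploratory test and a slightly narrower window. No additional biopsy is required. The restriction does not remove slow disease evolution in old tissue from untreated patients; the recorded baseline dates let a reader judge that.
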